The primary aim of this study is to assess the effectiveness of rural pediatric obesity treatment delivered virtually to family homes (iAmHealthy) compared to an active attention control group (control). This is a cluster randomized design, with schools being assigned to condition (iAmHealthy or control) and the 8 parent/child pairs at each school being assigned to the same condition. Having children and families from the same school participate in the same mHealth group allows us to target the unique environmental characteristics that are both barriers to and facilitators of success in iAmHealthy.

II. Research Plan and Design

A. Design and Intervention.

The intervention is a cluster randomized design as groups will be randomized by school. Schools will be contacted via a flyer sent to all 550 rural elementary schools in the state of Kansas. Schools will contact researchers via a toll-free number and given detailed instructions on how to complete the required human subjects training and earn Institutional Review Board approval. Recruited schools will be stratified by two key variables (school size, percent free/reduced lunch) and then assigned to one of the intervention groups, such that all children/families who sign up at each elementary school will be assigned by school as a single group to either iAmHealthy or control (i.e., randomization occurs at the school level, not at the individual level). Any subsequent schools will be waitlisted for participation the next year.

Once 6 schools are randomized, they will be sent research grade scales and stadiometers and trained by research staff in all measurement and intervention procedures. At this time school representativeness will be analyzed each year, and if schools are not representative on either of the key metrics, schools recruited the following year will be oversampled in order that schools reach a representative sample by the end of the 5-year study.

The iAmHealthy family-based intervention provides behavioral, nutrition, and physical activity topics (see Table 4 and Appendix A). The intervention has an 8-week intensive weekly intervention phase followed by a 6-month period of

Table 4. iAmHealthy Standard Int	Rurally Tailored Topics	
Goal Setting & Sticker Charts	Reading Food Labels	Decreased focus on fast food
Stop Light Diet Parent Health Behavior Changes	Energy Balance Use of Privileges	Increased focus on eating at social gatherings

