	Weeks 1-8	Weeks 9-12	Weeks 13-16	Weeks 17-20	Weeks 21-24	Weeks 25-28	Weeks 29-32			
iAmHealthy Intervention	8 weekly sessions	1 session	1 session	1 session	1 session	1 session	1 session			
	11 hours of homework help via remote technology									

in the area of pediatric obesity treatment, children who receive at least 25 contact hours over a 6-8 month period are significantly more likely to be successful than children who receive fewer hours.²²

B. Sample Criteria

- 1. Sample Size:
 - a. About 144 parent/child pairs (8 or more parent/child pairs at 18 schools). Approximately 175 parent/child pairs will be consented to have 144 children go on to enrollment.
- 1. Inclusion/Exclusion Criteria:
 - a. Inclusion Criteria:
 - i. Family lives in a rural area (city and/or county population <20,000)
 - ii. Child BMI >85th and <99th percentile
 - iii. Child in 2nd thru 4th grade
 - iv. Both child and parent speak English
 - v. Family is available at times intervention is offered
 - b. Exclusion Criteria
 - i. Child has physical limitation or receives and injury which significantly limits physical activity
 - ii. Child has significant medical issue known to the school (i.e. cancer)
 - iii. Child and/or parents have a significant developmental delay or cognitive impairment that is known to the school

- iv. Child has a sibling already enrolled in the program
- v. Family moves to a non-participating school

C. Enrollment, Consent, and Procedures.

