- 2. Child Body Mass Index z score (BMIz) and Parent Body Mass Index (BMI). To calculate child BMIzand parent BMI we will use standard formulas/equations. Height and weight will be assessed by fully trained onsite school representatives on standardized, calibrated equipment provided by the study. All staff will be trained in standard research anthropometric measurement protocol, including calibration techniques. Standing height will be assessed in

Table 6. Measures timeline.			
Primary Outcome Measures	Baseline	8 months	24 months
24 hour food recall (child)	Х	Х	Х
Physical Activity Monitors (child)	Х	Х	Х
Child BMIz/ Parent BMI ¹	Х	X	Х
R each			
Participation	Х	Х	
Structured Interviews with Non- participants		Х	
E fficacy			
HRQOL (parent, child)	Х	Х	Х
Parent Distress (parent)	Х	Х	Х
Peer Victimization (child)	X	Х	X
Child Depression (child)	Х	Х	х
Satisfaction (parent, child)		х	
Stigma (parent, child)		Х	
A doption			
Assess Representativeness of Participating Schools	Х		
I mplementation			
Attendance/Participation		Х	
Cost		Х	
Group Process		Х	
M aintenance			
Structured Interviews With Participating Schools		Х	
Other Measures			
Demographics (parent)	Х		
Food Insecurity	Х		
Post Questionnaire (parent)		Х	
Technology Feasibility (parent)	Х	Х	
$^{1}\mbox{Child BMIZ/Parent BMI will be taken monthly throughout}$	the 8 month into	ervention period	

triplicate via a Harpenden Holtain stadiometer, Model 603 (Holtain, Crymych, UK). Weight will be measured in triplicate on a portable SECA digital scale (SECA, Hamburg, Germany) after the participant has been asked to void. Parents and children will be measured with light clothing and no shoes.

Other Measures

1. *Demographics*. This questionnaire will ask about age, race, ethnicity, income, free/reduced lunch status, and parental education. We will also assess for the availability of home computers, high-speed internet access, tablets, smartphones, or other technology already present in the home that could be utilized for secure videoconference

- connections in future studies.

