Some outcomes will be analyzed using the multilevel model described above with a baseline covariate. These outcomes include Efficacy outcomes for parent and child reports of HRQOL, parent distress, child depression, and child peer victimization. A second set of outcomes involve tests of treatment condition differences where a baseline covariate is not available. These outcomes will be analyzed similarly with a multilevel model, however there will not be a level-1 covariate for the outcome at baseline. Outcomes to be analyzed in this manner include: parent and child satisfaction within Efficacy as well as attendance, participation, and cost from Implementation. The stigma outcome within Efficacy will be analyzed by comparing the proportions reporting child stigmatization between treatment conditions. This will be done for both child and parent report. A third set of outcomes will be examined descriptively. These outcomes include participation from Reach as well as descriptions of the barriers obtained in the qualitative analysis, school-level demographics from Adoption, engagement from Implementation, the number of schools retaining intervention components and summaries of factors related to maintenance from Maintenance. Participant demographics, reported food insecurities, and technological feasibility will also be examined descriptively.

Missing Data. While attrition and incomplete data may be unavoidable, the deleterious effects missing data may have on our results can be mitigated through a combination of careful data collection and thoughtful analysis. Full information maximum likelihood estimation which uses all available data to build a multidimensional likelihood function for each highest-level unit (schools) will be used for the multilevel models. For variables brought into the likelihood function, any missing cases are assumed missing at random, which means random only after conditioning on model predictors and the observed outcomes. Reasons for student departure (e.g., dropout versus changing schools) can be tracked and included as model predictors to help reduce the bias that might otherwise be created.

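### The stigma comparison makes no stated allowance for school, the unit that was randomised (minor)

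*Combined protocol and SAP*

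**What the plan says.** Section II.A (Design and Intervention) states that "randomization occurs at the school level, not at the individual level". Section II.B (Sample Criteria) plans "8 or more parent/child pairs at 18 schools", about 144 pairs in total.

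Section II.E (Statistical analyses) then sorts the non-primary outcomes by method:

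- Multilevel model with a baseline covariate: "Efficacy outcomes for parent and child reports of HRQOL, parent distress, child depression, and child peer victimization".
- Multilevel model without one. The group is introduced by "A second set of outcomes involve tests of treatment condition differences where a baseline covariate is not available" and its members follow: "Outcomes to be analyzed in this manner include: parent and child satisfaction within Efficacy as well as attendance, participation, and cost from Implementation".
- Stigma, in a sentence of its own straight after that list: "The stigma outcome within Efficacy will be analyzed by comparing the proportions reporting child stigmatization between treatment conditions". The next sentence adds "This will be done for both child and parent report".
- A descriptive group, which does not include stigma.

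Table 6 (section II.D) schedules stigma at 8 months only, so it has no baseline value. No test, interval, random effect, robust variance or school-level summary is named for it anywhere in the document.

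**The concern.** Stigma meets the condition that defines the second multilevel group, since it is compared between conditions and has no baseline value. It is nevertheless left out of that group's list and given a different method. An analyst who follows the sentence literally would pool the children in each arm and compare two proportions, treating the 8 children from one school as independent.

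Clustering is plausible here. The pairs from a school share that school and, in the intervention arm, one group; the child item asks about being made fun of, and schoolmates are shared. If school is ignored, differences between schools are read too often as differences between arms, and the confidence interval is too narrow.

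This is the item that asks directly about harm from taking part. A false difference could suggest that the programme stigmatises children, or that it protects them. Section II.E applies the same approach to the intention-to-treat and completer analyses, so with two reporters the gap touches 2 × 2 = 4 comparisons.

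**Working it through.** **Plan's own figure.** 18 schools × 8 pairs = 144, which matches section II.B. Section II.C does not enrol families beyond the first 8 at a school, so 8 is used as the cluster size.

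**Assumed, because the documents do not give them.** Equal split (9 v 9 schools, 72 pairs per arm); two-sided 5% test; intraclass correlation (ICC) 0 to 0.10; proportion reporting stigma 5% to 30%, the same in both arms under the null; no attrition unless stated.

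**Formulas.** Design effect DE = 1 + (8 − 1) × ICC. Effective sample size = 144 / DE. Approximate type I error of a test that ignores school = 2 × [1 − Φ(1.96 / √DE)].

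At ICC 0.05, for example: DE = 1 + 7 × 0.05 = 1.35; 144 / 1.35 = 107; 1.96 / √1.35 = 1.687; type I error = 9.2%.

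The formula was checked by beta-binomial simulation (100,000 trials per setting). It compared a pooled chi-square without continuity correction with a pooled-variance t test on the 18 school proportions (16 df). Ranges are over 5–30% prevalence.

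| ICC | DE | Effective N | Formula | Pooled chi-square | School-level t test |
|---|---|---|---|---|---|
| 0 | 1.00 | 144 | 5.0% | 4.8–5.1% | about 5% |
| 0.02 | 1.14 | 126 | 6.6% | 6.3–6.9% | 5.0–5.1% |
| 0.05 | 1.35 | 107 | 9.2% | 8.7–9.6% | 4.4–5.1% |
| 0.10 | 1.70 | 85 | 13.3% | 12.6–13.6% | 3.5–5.1% |

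Repeat runs agree to within simulation error.

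**Sensitivity** (ICC 0.02 / 0.05 / 0.10):

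- Rare reports, 2% prevalence: chi-square 3.7% / 5.2% / 7.7%; Fisher's exact test at most 1.7%.
- Fisher's exact test at 5–30% prevalence: 2.1–4.6% / 3.3–6.5% / 5.6–10.3%.
- 80% of children retained: chi-square 5.6–6.4% / 7.4–8.5% / 10.1–11.9%.
- 10 v 8 schools at 10% prevalence: chi-square 6.9% / 9.4% / 13.7%, against 6.6% / 9.3% / 13.4% for 9 v 9 in the same run. An uneven split does not remove the problem.

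**Interval coverage** at a true 20% v 5%: pooled Newcombe interval 94.1% / 91.7% / 87.6%; interval from the school-level t test 94.3% / 94.3% / 94.1%.

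**The case against.** A reader might infer that the plan has chosen an unadjusted chi-square test. It has not. It names no test, and comparing proportions is compatible with a clustered comparison. Section II.E also refers back to a multilevel model set out earlier, and the public text contains no such description. A general statement about school could have stood there and could cover stigma. The error rates above therefore describe one way of carrying out the sentence, not something the plan commits to. This stands and limits the claim. It does not remove it, because the text as it is gives stigma a separate method and leaves it out of both multilevel groups and the descriptive group.

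A reader might also infer that the trial's other analyses ignore school. The documents do not support that: the missing-data paragraph of section II.E names schools as the highest level of the multilevel models.

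The size of the effect rests on assumed inputs. With ICC 0.02 or rare reports it is small or absent, and Fisher's exact test would stay below 5% at ICC 0.02. Equal prevalence may also be the wrong null for the child item, which asks about having been in iAmHealthy. That is the name of the intervention arm as well as of the study, and control children who read it as the arm could hardly answer yes. Both points stand.

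Finally, stigma is not a primary outcome. Peer victimization and obesity-specific quality of life, whose child version has a teasing and marginalization scale, measure overlapping harm and do get multilevel models. This also stands, and it sets the severity.

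**Conclusion.** The concern holds as a gap in the plan, of minor severity. Section II.E states no allowance for school in the stigma comparison, although school is the randomised unit and the section's other tested outcomes are modelled with it.

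The consequence is conditional on school being left out of the calculation. Then a pooled chi-square has a type I error of about 6–7%, 9–9.5% and 13–14% at ICC 0.02, 0.05 and 0.10, on the assumptions listed (9 v 9 schools of 8, 5–30% prevalence, two-sided 5%). There is no inflation at ICC 0, and little or none at 2% prevalence with an ICC of 0.05 or less. Nothing is claimed about the primary outcomes or about the form of the multilevel model.

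**What to change.** Replace the stigma sentence in section II.E with one that makes school the unit for both the p-value and the interval. For example:

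> For child report and for parent report separately, the proportion reporting stigmatization in each school will be compared between conditions by a two-sample t test on the school proportions (number of schools minus 2 degrees of freedom; 16 with 18 schools), with the 95% confidence interval from the same test. Counts by condition and school will always be shown beside it.

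A cluster-adjusted model with a small-sample correction would also do, and would sit closer to the rest of the section.

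The test should not depend on a minimum number of reports. A threshold taken from a pooled Fisher test would itself ignore school: 5 v 0 reports spread over five schools give p = 0.006 under the school-level t test. A cut-off of 6 reports would suppress the test in about 29–34% of trials at 5% prevalence.

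The change costs one sentence and needs no new data. The downsides of the t test are:

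- Wider intervals: at 20% v 5% and ICC 0.05, mean width 25.8 against 21.7 percentage points.
- Less apparent power: about 64% against 78% in that setting, where the chi-square runs at about 9% type I error; 76% against 81% at ICC 0.
- Equal weight to schools whatever their final size, and no use of the randomisation strata.
- Coverage of 92.6–93.1% if the higher-risk arm has 8 schools and the other 10.
- A conservative test when reports are rare.

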Schools will send home letters to parents and families explaining the study and interested parents will be invited to call the researchers via a toll-free number with any questions. Parents will then come in for an orientation visit at the school and meet with the onsite school representative. In the event of school closure (ie. COVID-19 outbreak), these consenting sessions will take place remotely over the Zoom teleconferencing app instead of in person. At this meeting, the onsite school representative will go over the e-consent form with the parent and child. The e-consent will be housed in REDCap, and school study personnel will pull up the consent form on an iPad or a computer for the parent to review. The parent, child, and the onsite school representative will e-sign the consent form either with their finger or a mouse, depending on if they are using an iPad or a non-touch screen desktop computer. The consent form reads that a copy of the signed consent form will be mailed to them. KUMC study staff will print the signed consent form in REDCap and mail this form to the family once all the families in the school cohort have consented (which will be approximately a 1–2-week window). We will also have paper consent forms available in case of technology difficulties. Onsite school representative will only be permitted to use a paper consent process in the rare occurrence of internet or REDCap outage. If a paper consent is signed, a signed copy may be given to the parent at the time of consent. Paper consent forms would then be securely shipped to KUMC via FedEx express mail.

After parents and children are consented, the onsite school representative will measure height and weight and calculate BMI percentile for each child to assure that they qualify for the study. Schools will each recruit 8 target parent/child pairs. If they cannot recruit 8 parent/child pairs, the school will be waitlisted until such a time as they can. If more than 8 families express interest and complete enrollment procedures, if the school is assigned to iAmHealthy, those beyond the initial 8 will be offered a paper copy of the intervention manual to complete on their own and will not be enrolled as subjects (for the newsletter group, they will be sent the newsletter but will not be enrolled as subjects).

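### Full maximum likelihood is named for multilevel models with only 18 randomised schools and no small-sample method; with a normal reference, type I error would be about 6–8% at ICC 0.02–0.20

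*Combined protocol and SAP*

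**What the plan says.** Section II.A makes the school the unit of allocation: "randomization occurs at the school level, not at the individual level". Section II.B plans "8 or more parent/child pairs at 18 schools", about 144 pairs in all. Section II.C fixes the working size per school, "Schools will each recruit 8 target parent/child pairs", and does not enrol families beyond the first 8.

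Section II.E assigns most tested outcomes to multilevel models, some with a baseline covariate and some without. Its Missing Data paragraph names the estimator: "Full information maximum likelihood estimation which uses all available data to build a multidimensional likelihood function for each highest-level unit (schools) will be used" for those models. The reason given is that all available data enter the likelihood under missing at random.

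The text does not mention restricted maximum likelihood (REML), Kenward-Roger or Satterthwaite degrees of freedom, a between-school t reference, or any other small-sample method. Nor does it say that tests will use a normal reference. Alpha, sidedness, the ICC and the split of schools between arms are not given. Section II.E also says "Some outcomes will be analyzed using the multilevel model described above with a baseline covariate", but no description of that model precedes the sentence in the available text.

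**The concern.** Arm varies only between schools, so its standard error rests on the spread of 18 school means. Full ML divides the between-school sum of squares by 18, whereas 16 is the divisor that allows for the two arm means. The estimated variance is therefore too small. If the estimate is then compared with a normal or chi-square reference, as many programs do by default for ML, the uncertainty in that variance is ignored as well. Both errors make the arm effect look more precise than it is.

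At stake is the error rate for HRQOL, parent distress, child depression, peer victimisation, satisfaction and the other outcomes assigned to these models. It affects both the intention-to-treat and the completer analyses, because section II.E uses the same approach for each.

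**Working it through.** **Inputs from the plan.** 18 schools (II.B); 8 pairs per school (II.C); allocation by school (II.A); full ML (II.E). The plan's own size reproduces: 18 × 8 = 144.

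**Assumptions, because the plan is silent.** 9 schools per arm; two-sided 5% test; one follow-up value per child; ICC from 0 to 0.20; normal, likelihood-ratio and t(16) references.

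**Formulas.** Take a balanced random-intercept model with total variance 1 and m = 8. The school-mean variance component is λ = (1 − ICC) + 8 × ICC, and the variance of the arm difference is (λ/8)(1/9 + 1/9). ML estimates λ by SSB/18 and REML by SSB/16, where SSB is the between-school sum of squares within arms. If that estimate falls below the within-school mean square (on 18 × 7 = 126 df), the school variance is set to zero and the two sources are pooled.

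**Limit when the school variance is never truncated at zero.**
- Standard error factor: √(16/18) = 0.943.
- ML, normal reference: reject when |t(16)| > 1.96 × 0.943 = 1.848, probability 8.3%.
- ML, t(16) reference: reject when |t(16)| > 2.120 × 0.943 = 1.999, probability 6.3%.
- Width of the ML normal interval relative to the REML t(16) interval: 1.96 × 0.943 / 2.120 = 0.87.

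**Type I error with truncation** (1,000,000 simulated null trials per ICC):

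| ICC | ML, normal | ML, likelihood ratio | ML, t(16) | REML, normal | REML, t(16) | Mean ML SE / true SE |
|---|---|---|---|---|---|---|
| 0 | 4.7% | 4.2% | 3.2% | 4.2% | 2.9% | 1.03 |
| 0.01 | 5.2% | 4.7% | 3.6% | 4.6% | 3.2% | 1.01 |
| 0.02 | 5.8% | 5.1% | 4.1% | 5.1% | 3.5% | 0.99 |
| 0.05 | 6.8% | 5.9% | 5.0% | 5.8% | 4.2% | 0.96 |
| 0.10 | 7.8% | 6.6% | 5.8% | 6.5% | 4.7% | 0.94 |
| 0.20 | 8.2% | 6.8% | 6.2% | 6.7% | 5.0% | 0.93 |

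At low ICC the school variance is often truncated to zero, and the pooled estimate offsets the ML bias. At higher ICC truncation is rare and the rates approach the limits above. The REML normal column shows that changing the estimator alone is not enough: the reference distribution matters too.

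**Sensitivity.** With a baseline covariate and an assumed 20% of outcomes missing at random (20,000 trials per setting), ML with a normal reference gives 5.0%, 5.5%, 6.6% and 8.0% at ICC 0, 0.01, 0.05 and 0.10. The balanced results are not an artefact of complete data.

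**The case against.** The strongest reply is that the plan never chooses a normal reference. It omits the reference distribution, and the paragraph is about missing data rather than tests. An analyst could fit by ML and still use t(16); the rate then stays at or below 5.0% up to ICC 0.05 and reaches only 5.8–6.2% at 0.10–0.20. If the ICC is 0–0.01, even the normal reference gives 4.7–5.2%, and the ML standard error is on average not too small. All of this stands, so the inflation is conditional. It cannot be dismissed either: the plan gives no ICC, and section II.A has the 8 families from a school attend one group, built around that school's own barriers and supports. That is a plausible source of within-school correlation.

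It also stands that the model said to be described above is not in the available text. The supportable statement is that no small-sample method appears there, not that one was considered and rejected.

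A reader might infer a larger error from the stratification by school size and percent free/reduced lunch in II.A. If two school-level covariates were added in the sensitivity setting, ML with a normal reference would give 7.9% at ICC 0.05 and 9.0% at 0.10. But the plan names these variables for stratification and representativeness, not as model terms, so those figures are hypothetical.

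The missing-data rationale does not require ML. REML mixed models also use every observed outcome under missing at random. Full ML can additionally accommodate missing covariates, but that matters little for the baseline covariate, because the intention-to-treat set in II.E requires complete baseline measures.

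**Conclusion.** The point holds in conditional form and is a should-fix. The plan names full ML for a trial with 18 randomised schools and states no small-sample inference. With a normal reference, type I error is about 6–8% at ICC 0.02–0.20, an excess of roughly 1 to 3 percentage points, and the mean standard error is 1–7% too small. This rests on 9 schools per arm, 8 pairs per school and a two-sided 5% test, none of which contradicts the plan, and on an ICC that the plan does not give.

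A reader might conclude that every test in II.E has a false-positive rate above 5% and that every interval is too short. The documents do not support that. The result depends on the unstated ICC and reference distribution, and the stigma outcome is compared as proportions rather than by a multilevel model.

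**What to change.** Replace the estimator sentence in II.E with wording to this effect: multilevel models will be fitted by REML using all available observations under missing at random; arm effects will be tested, and 95% confidence intervals formed, with Kenward-Roger or Satterthwaite degrees of freedom, or with a t reference on between-school degrees of freedom (16 with arm as the only school-level term). If school-level covariates are later added, the between-school degrees of freedom should fall by one for each.

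With t(16), REML held the type I error between 2.9% and 5.0% across ICC 0–0.20. Kenward-Roger and Satterthwaite were not simulated here.

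The change is one sentence and a software setting. Where the school variance is not truncated, REML t(16) intervals are about 15% wider than ML normal intervals (1/0.872 = 1.147) and about 6% wider than ML t(16) intervals (1/0.943 = 1.060). At ICC 0–0.01 the test is mildly conservative, at about 3%, with some loss of power.
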